11.4 Exploratory or Tertiary endpoints/outcomes

N/A

11.5 Objectives and End Points Summary

Primary Objective	Primary Endpoint	Outcome Measures		
To determine whether	48-hour SOFA score	SOFA Score		
artesunate improves outcomes				
in patients with trauma				
haemorrhage				
Secondary Objective	Secondary Endpoints	Outcome Measures		
To determine effects of	Maximum SOFA score	SOFA Score		
Artesunate on organ failure	Prolonged organ failure	CTCOFR score		
	Days on organ support			
	Mean SOFA score (Day 2-5)			
To determine effects of	Incidence of acute lung injury	Berlin Definition of ALI		
Artesunate on lung injury				
To determine effects of	Incidence of acute kidney	RIFLE Score		
Artesunate on kidney injury	injury			
To determine effects of	Incidence of infection	Cole et al. Definitions		
Artesunate on infection				
To determine effects of	Number of ventilation free	Number of ventilation free		
Artesunate on ventilator	days	days		
requirements				
To determine effects of	Total length of hospital stay	Total length of hospital stay.		
Artesunate on hospital stay				
To determine effects of	Total length of critical care	Total length of critical care		
Artesunate on critical care stay	stay	stay		
To determine effects of	Mortality (discharge, 28 day	Mortality (discharge, 28 day		
Artesunate on mortality	and 90 day).	and 90 day).		
To determine effects of	Serious adverse event rate in	SAE rate in first 28 days		
Artesunate on patient safety	first 28 days			
To determine the impact of	Alive and free of multiple	48-hour SOFA score		
Artesunate on early survival	organ failure (defined as	48-hour mortality		
	SOFA≤5) at 48 hours			

11.6 Trial Design

This is a single-centre, randomized, placebo-controlled, parallel group study with a sequential groupdosing regimen (adaptive design). Its aim is to evaluate the safety and efficacy of Artesunate treatment compared to placebo, in addition to standard treatment, in severely injured trauma patients with traumatic hemorrhage. All subjects will be managed in accordance with local guidelines for traumatic hemorrhage.

Subjects will be assessed for eligibility upon arrival to the hospital. Due to the urgent/emergency nature of the intervention subjects will be recruited within 4 hours of their injury and within 2 hours of admission to the accident and emergency department. Eligible patients therefore need to be consented very soon after admission. As most, but potentially not all, subjects will be incapacitated at time of eligibility, consent can be obtained from relatives or if no relatives are present two

doctors (one independent of the trial) will decide on consent. If and when the subject regains physical and mental capacity they will be provided written information on the trial and will be given the opportunity to ask questions, informed consent will be sought for continuation in the trial. For any subject included but did not regain full capacity, consent will be sought from a relative or other appropriate representative for continuation in the trial.

Subjects will be randomized to one of three groups:

- Placebo arm (n = 35)
- Low Dose intervention arm: active drug 2.4mg/kg (n=35)
- High Dose intervention arm: active drug 4.8mg/kg (n=35)

The trial will be divided into two stages. The first stage will enroll patients into the Placebo (n=17) and Low Dose intervention arms (n=35), following which an interim analysis will be performed. The analysis will be limited to an analysis of safety data between the two groups. Provided there are no issues regarding safety or toxicity, the study will continue with the second phase enrolling patients into the high dose intervention arm (n=35) or placebo (n=18).

Each subject will be dosed and then remain in the study for 28 days or until they are discharged. There will be a 90-day follow-up though this will be conducted using data obtained via the NHS spine services (Health and Social Care Information Centre).

Subjects who do not complete the primary outcome end-point at 48-hours (e.g. due to death or discharge) will be replaced. Variables will be evaluated at different time points from screening through day 28 as per the schedule of events.

Adverse events (AEs) and serious adverse events (SAEs) will be reviewed by the trauma research fellow (who is a clinician) on a daily basis from the point of dosing throughout the 28-day subject participation in the trial. Please see Section 17 for further details.

The following will be determined at various points throughout the trial SOFA score, renal injury, lung injury, infection rate, the number of mechanical ventilation days, RRT days, vasopressor days, CTCOFR score, ACCU length of stay and the hospital length of stay.

11.7 Study Setting

A single-centre study conducted in an NHS Major Trauma Centre.

12.0 Eligibility Criteria

12.1 Inclusion Criteria

A subject will be eligible for the study if they meet the following criteria:

- Adult male and female trauma patients over 16 years of age.
- Activation of the local massive haemorrhage protocol (activation criteria are: systolic blood pressure <90 mmHg, AND suspected haemorrhage, AND minimal response to small volume fluid resuscitation).
- Patients with active, ongoing haemorrhage.
- Agreement is provided on behalf of incapacitated patients by Personal Legal Representative or Professional Legal Representative (i.e. trauma team leader).

12.2 Exclusion Criteria

A patient will not be eligible for the study if they meet any one of the following criteria:

- Time of admission more than 2 hours after the time of injury.
- Time of drug administration not attainable within 4 hours of injury.
- Subject not expected to survive more than 48 hours.
- Evidence of severe traumatic brain injury (GCS 3 at scene).
- Known pregnancy.
- Suspected non-haemorrhagic cause of shock.
- Massive haemorrhage protocol activation more than one hour after arrival.
- Concurrent participation on another Clinical Trial of an IMP.
- Breastfeeding females.
- Known allergy to Artesunate.

NOTE: Participants are considered not of child bearing potential if they are surgically sterile (have undergone a hysterectomy, bilateral tubal ligation, or bilateral oophorectomy) or they are postmenopausal.

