13.2 Participant identification

The trauma research fellow will attend all trauma admissions to the accident and emergency resuscitation department in order to screen participants for potential enrolment according to the study inclusion and exclusion criteria.

The trauma research fellow is a clinician by training, but not a member of the clinical team attending to the participant. This is due to the critical condition of participants, meaning that it is unlikely that a treating clinician will concurrently be able to provide the necessary care for the patient whilst also undertaking the research screening and enrolment procedures.

However, once the trauma research fellow deems a participant to be eligible for enrolment, they will confirm eligibility with the clinician leading the care for the patient (i.e. the trauma team leader) prior to enrolling the participant into the study. Our study centre and research team has experience in conducting similar screening procedures successfully in previous studies.

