13.4 Screening Procedures

Patients will be assessed for eligibility to enter the trial according to the defined inclusion/exclusion criteria upon arrival at the hospital. This will include a pregnancy test for all females of childbearing age. If patients are assessed to be eligible, consent for entry into the study will be sought. Data will be collected on all patients who are screened for eligibility on the study screening-log by the Trauma Research Fellows.

A screening log will be completed, which will record all patients considered for eligibility to the trial. The log will include date and time of screening, and the participant age, gender, and reasons for non-enrolment. The screening log will include patients approached but in whom consent was not obtained for the trial (with reasons). The screening log data will be reviewed at regular intervals.

The trauma research fellow and research assistant are responsible for completing the screening log after an eligible patient is identified and considered for participation in the trial

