13.8 Trial Schedule

13.8.1 Schedule of Treatment for each visit

The following procedures will be conducted after arrival of the subject at the hospital.

Screening:

- Assess eligibility (refer to inclusion/exclusion criteria).
- Check that written agreement has been given to participate in the study in the form of a signed and witnessed informed consent form.
- Review medical and trauma history.
- Pregnancy test: by either urinary, serum, or point-of-care (see Fromm *et al.* 2012) testing of human chorionic gonadotrophin (hCG) for women of childbearing age.
- Vital signs (heart rate, blood pressure, respiration rate, oxygen saturations, body temperature, Glasgow Coma Score GCS).
- Dispense IMP in accordance with the randomization sequence.

Dosing:

• Body weight

- IMP administration
- Obtain blood samples for PK/PD analysis
- Monitor AEs and SAEs.

The following procedures will be conducted after dosing of the subject.

0 to 12 hours

- Blood sampling for PK/PD analysis
- Record baseline arterial blood gas.
- Monitor and record AEs and SAEs.
- Sequential organ failure assessment (SOFA) score.
- Renal injury, as per the risk, injury, failure, loss of function, endstage renal failure (RIFLE) score.
- Lung injury as per the Berlin definition.
- Infection rate.
- Number of ventilation free days.
- Renal Replacement Therapy (RRT) days.
- Vasopressors days.
- Composite time to complete organ failure (CTCOFR) score.
- Total length of critical care stay.
- Total length of hospital stay.

0 to 48 hours:

- Monitor and record AEs and SAEs.
- Record safety blood results.
- Record 24 hour fluid and transfusion requirements.
- Record concomitant medications.
- Sequential organ failure assessment (SOFA) score.
- Renal injury, as per the risk, injury, failure, loss of function, endstage renal failure (RIFLE) score.
- Lung injury as per the Berlin definition.
- Infection rate.
- Number of ventilation free days.
- Renal Replacement Therapy (RRT) days.
- Vasopressors days.
- Composite time to complete organ failure (CTCOFR) score.
- Total length of critical care stay.
- Total length of hospital stay.
- Record whether patient is alive and free of multiple organ failure (SOFA <5) at 48 hours

49 hours to Day 7:

- Monitor AEs and record SAEs.
- Record safety blood results.
- SOFA score.
- Renal injury, as per the RIFLE score.
- Lung injury as per the Berlin definition.
- Infection rate.
- Number of ventilation free days.
- RRT days.

- Vasopressors days.
- CTCOFR score.

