13.8.3 Trial assessments

Medical History

The medical and trauma history will be conducted at screening and should include (but not be limited to) demographic information, subjects' medical history with an emphasis on the trauma, current medication, past medication and allergies. This will be ascertained as part of the subjects' initial clinical assessment by the trauma team, and the Trauma Research Fellow. The known medical history must be documented in the subject's notes (the on-site source document) prior to IMP administration and also recorded in the CRF. Any further medical history ascertained subsequent to the initial assessment will be derived from the subjects' notes during the assessment phase.

Vital signs

Vital signs will be recorded at baseline and at PK/PD sampling points. They will also be monitored for 28 days as part of the SAE assessment process.

Systolic and diastolic blood pressures will be recorded using a standard sphygmomanometer reading or by invasive arterial monitoring (where this has been inserted as part of routine clinical care). Pulse rate and oxygen saturations will be measured by pulse oximetry or by arterial monitoring as above. Respiration rate will be assessed by observation as breaths per minute; and a tympanic body temperature measure will be used, unless other methods (e.g rectal monitoring) are in place for continuous clinical monitoring. GCS will be recorded from the subject notes or assessed clinically.

Pregnancy test

Prior to administration of any IMP a pregnancy test will be undertaken on all women of childbearing potential.

Note: The subject must not be dosed if any tests are positive.

Body weight

Body weight will be estimated to the nearest 10kg.

PK/PD Blood samples

Subjects will have 10mls of blood drawn to determine the plasma levels of Artesunate and its metabolite DHA (PK-PD study in man) at the following time points:

- At hour 0 (within 10 minutes) immediately prior to IMP dosing
- 5 (±1 minute) minutes after the start of IMP infusion
- 30 (±2 minutes) minutes after the start of IMP infusion
- 1 (±5 minutes) hours after the start of IMP infusion
- 4 (±20 minutes) hours after the start of IMP infusion
- 12 (±30 minutes) hours after the start of IMP infusion

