13.9 Withdrawal criteria

Every reasonable effort will be made to maintain protocol compliance and to retain patient participation in the study consistent with the provisions of informed consent and good clinical practice. The following are potential reasons why a patient may be withdrawn from the study:

- 1. Withdrawal of consent: the patient, the patient's authorised representative, independent physician, or designated individual who had provided initial consent to enter the study may withdraw consent at any time throughout the duration of the trial, without prejudice to future medical care and treatment.
- 2. Retrospective exclusion: If a patient is deemed to not meet one or more of the inclusion/exclusion criteria in retrospect they will be withdrawn from the study.
- 3. Major protocol deviation from the study design by the subject, observed or suspected by the investigator.
- 4. Adverse event.
- 5. Administrative: the sponsor or monitoring committees decide to terminate or discontinue the study.
- 6. The subject's health would be jeopardised by continued participation and is withdrawn at the discretion of the investigator.

Data Collection And Follow-Up For Withdrawn Subjects

If a patient is withdrawn from the study before receiving IMP but after randomisation, any ongoing SAE experienced by the patient, which are not injury- or standard-treatment related, will be followed to resolution but no other safety or efficacy assessments will be conducted.

Patients who withdraw from the study after receiving IMP should be followed for safety by conducting safety assessments through to the end of day 28. If a patient who withdraws has develops an SAE during the monitoring period, every effort must be made to follow such events until satisfactory resolution is obtained or until further follow-up is no longer warranted.

Any samples obtained from withdrawn participants will be discarded in accordance with the Bart's Health NHS Trust standard procedures.

Replacement Of Subjects

Subjects who do not complete the primary outcome end-point at 48-hours (e.g. due to death or discharge) will be replaced. Subjects who withdraw from the study at any time point will also be replaced. Withdrawn participants will not be permitted to re-enter the study.

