15.14 Dispensing of IMP

Each member of staff who administers the IMP will sign the local pharmacy (Barts Health Pharmacy, Royal London Hospital) dispensing-log in order to track the IMP. All trial team members will have had study specific training in order to administer the IMP, which will be recorded in a delegation log.

Five doses of the IMP will be stored in a secured limited-access area, in the Trauma Sciences Lab situated on Ward 12D in the Royal London Hospital, Barts Health NHS Trust. This is to allow immediate access of the IMP to Trauma Research Fellows' upon enrollment of a subject as administration time critical.

Trial team members will perform a daily check on the Ward IMP supply to ensure stock is maintained. The Trauma Research Fellow/Assistant will be responsible for contacting pharmacy for re-supply, and this will also be recorded.

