15.16 Known drug reactions and interaction with other therapies

Artesunate is rapidly and extensively converted to dihydroartemisinin (DHA), the active metabolite, primarily by plasma and erythrocyte esterases. DHA elimination is also rapid (half-life approximately 45 min) and the potential for drug-drug interactions appears limited. In vitro drug-interaction studies have demonstrated minimal effects of artesunate on cytochrome P450 isoenzymes. Few clinical drug-drug interaction studies have been performed, however no clinically significant interactions have been identified (See Investigators Brochure, Version 1.0, Dated 6th January 2016).

There are no prohibited concomitant medications or therapies. Contraindications include:

- Serious adverse reaction or hypersensitivity to artesunate or any other artemisinin.
- Pregnancy due to the risk of spontaneous abortion, especially during the first trimester.

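### Exclusion criterion 12.2 carries over only part of the artemisinin contraindication in 15.16 (lowest severity, patient safety only)

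*Protocol*

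**What the plan says.** Section 12.2 makes a patient ineligible if any one of its listed criteria is met. The only entry about earlier reactions to the drug is "Known allergy to Artesunate". The list has no general entry for contraindications and does not refer to 15.16.

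Section 15.16 names two contraindications. One is pregnancy. The other is "Serious adverse reaction or hypersensitivity to artesunate or any other artemisinin".

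The steps that decide who enters the trial point to the list in 12.1 and 12.2:

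- Section 13.2 has the research fellow "screen participants for potential enrolment according to the study inclusion and exclusion criteria".
- Section 13.4 has patients "assessed for eligibility to enter the trial according to the defined inclusion/exclusion criteria".
- The screening steps in 13.8.1 refer to the same criteria.
- The retrospective-exclusion rule (13.9, reason 2) applies to patients found to "not meet one or more of the inclusion/exclusion criteria in retrospect they will be withdrawn from the study".

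**The concern.** The contraindication is wider than the exclusion in two ways. It covers the whole artemisinin class rather than artesunate alone, and it covers any serious adverse reaction rather than allergy alone. Staff who apply 12.2 as written could enrol and randomise a patient whom the protocol's own drug section says should not receive the drug.

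What is at stake is patient safety, on a small scale. Eligibility is settled in an emergency: under 15.13 the bolus is due within 4 hours of injury and 2 hours of admission. A known contraindication is best caught by the list that staff are told to use, before randomisation, rather than at the point of injection.

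**Working it through.** No arithmetic applies. The check sets the two sections side by side and then looks for any other rule that closes the gap.

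**Step 1: split the contraindication into its parts.** It joins two kinds of history with two drug categories, giving 2 × 2 = 4 combinations. Allergy in 12.2 is read as equivalent to hypersensitivity in 15.16.

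| Known history | Artesunate | Another artemisinin |
|---|---|---|
| Hypersensitivity | 15.16 and 12.2 | 15.16 only |
| Serious non-allergic reaction | 15.16 only | 15.16 only |

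Section 12.2 covers one of the four and leaves three uncovered. A mild non-allergic reaction is not contraindicated by 15.16, so it is no part of this point.

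**Step 2: compare the other contraindication.** Pregnancy appears in 15.16 and also in 12.2. It is tested at screening (13.4, 13.8.1), and 13.8.3 forbids dosing after a positive test. That contraindication was carried through to eligibility in full. The artemisinin one was carried through in part.

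**Step 3: look for a rule elsewhere that extends the list.**

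- Section 13.8.3 requires a medical history that includes "current medication, past medication and allergies", documented before dosing. It attaches no exclusion to what is found.
- Section 13.2 asks the trauma team leader to confirm eligibility, which leads back to the same list.
- Section 13.3.6 has two doctors, one independent of the trial, decide on enrolment when no relatives are present. They too consider the eligibility criteria, together with any known views of the patient.
- Section 15.15 stops the injection if a toxic reaction occurs while it is being given. It does not address earlier history.
- Section 22.5 forbids enrolment against the eligibility criteria or other restrictions set by the protocol, but 15.18 states that there are none of the latter. It does not clearly bring in 15.16.
- Section 13.9, reason 2, uses the inclusion and exclusion criteria, so it would not pick up the three uncovered combinations. Reason 6 allows the investigator, at discretion, to withdraw a subject whose health continued participation would put at risk. The same section provides for withdrawal between randomisation and dosing, and for replacement.

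**Result.** Several provisions could stop such a patient from being dosed. None of them makes the patient ineligible.

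**The case against.** The strongest reply is that nothing here is contradictory. Section 15.16 is part of the same protocol and lists contraindications to the drug, so an investigator who follows the whole document would not dose such a patient. Section 15.14 adds that "All trial team members will have had study specific training in order to administer the IMP". On this view the point is a drafting preference. The first part stands: both sections can be followed together, and a reader who infers a conflict between them goes further than the text allows. What does not follow is that the list needs no change. Enrolment and randomisation are governed by 12.1 and 12.2, and the treatment of pregnancy shows that the protocol does put contraindications into that list.

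A reader might also infer that 13.9 offers no way out once such a patient is randomised. The text does not support that either, because reason 6 is available. It is discretionary, so it mitigates the gap without closing it.

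The third reply is that the change would rarely alter a decision. Artesunate is not licensed in the UK (15.2), most patients are incapacitated at screening (13.3.6), and a relevant history will seldom be known. This stands in full and is why the point carries the lowest severity. Rarity alone is not a reason to leave the wording, however. Section 9.1 cites only four cases of anaphylaxis to artesunate, and the protocol still lists artesunate allergy as an exclusion.

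**Conclusion.** The point holds as an incomplete carry-over of a contraindication from 15.16 to 12.2. Three of the four combinations in 15.16 are missing from the eligibility list, and the existing safeguards reduce the consequence without removing the gap. It concerns patient safety only. Sample size, power, endpoints and analysis are unaffected.

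No number of affected patients is offered. A reader might be tempted to derive an upper bound from the review in 9.1 that found no serious adverse events among 9,241 artesunate-treated subjects. That would not be reliable. It is a single pooled review. The same section separately cites four cases of anaphylaxis, and 15.15 describes a fatal overdose. The figure would also say nothing about other artemisinins, for which the protocol gives no rate, and it would need the share of patients previously exposed, which the protocol does not give. All that can be said is that 9.1 describes allergic reactions to the class as rare and that such histories will seldom come to light at screening.

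The conclusion rests on reading allergy and hypersensitivity as the same thing, and on the eligibility list being applied as written. The items of the CRF checklist are not shown in 20.7, so its wording may already be wider.

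**What to change.** Replace the bullet in 12.2 with the word Known followed by the wording of 15.16: "Serious adverse reaction or hypersensitivity to artesunate or any other artemisinin". Use the same wording for the corresponding item in the CRF eligibility checklist named in 20.7. Screening, team-leader confirmation and retrospective exclusion then pick up the full contraindication without further edits, because they already refer to the criteria.

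The cost is one bullet and one checklist item. The only downside is a very rare extra exclusion, and it arises only when the history is known.
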